The participating units in this collaborative clinical trial include: eight individual clinical centers, a Coordinating Center which includes a laboratory and CT scan reading center, the NINDS Division of Stroke and Trauma.

B. Participating Sites

1. Clinical Centers

Eight clinical centers will be responsible for recruiting the required number of patients, administering the study drugs, coordinating patient care, and collecting the information required by the trial protocol. The Principal Investigator is responsible for the overall conduct and performance of the clinical center. The organization of each clinical center will differ, but each clinical center will have one person specifically identified as the clinical coordinator and one person identified as the patient recruitment coordinator. The clinical coordinator will be responsible for such critical matters as checking Emergency Room logs, appointment scheduling, checking the completeness of forms, and arranging the shipment of blood specimens and CT data to the Coordinating Center.

2. Coordinating Center

The Coordinating Center will provide overall guidance and coordination of the data management, quality control, data analysis for the study, centralized measurement of fibrin and fibrin-fibrinogen degradation products and monitoring for safety. This will include preparation of the procedure manual, data collection forms and the various

reports. Although the primary responsibility for early recruitment is at the clinical centers, the Coordinating Center will assist in this effort, not only by monitoring the degree of success at the various centers, but also by holding meetings of the patient recruitment coordinators to develop recruitment strategies for each of the clinical centers and then monitoring the success of the implementation of these plans.

a. Coagulation Laboratory

Frozen plasma and serum will be sent from the clinical centers to the Coordinating Center coagulation laboratory. The coagulation laboratory at Henry Ford Hospital will receive and analyze frozen plasma samples for fibrinogen and frozen serum for the fibrinogen degradation products.

b. CT Reading Center

The clinical centers will send CT scan data to the Coordinating Center for reading. Although centers will have read the baseline scan to determine eligibility, these scans should also be sent to the Coordinating Center to be read. All clinical center sites will be asked to send data tapes and hard copies of each CT of the brain.

The initial interpretation will include:

- A description of the quality of the study
- Presence or absence of an infarct
- The arterial or venous distribution of the infarct.
- The infarct and brain volume.
- Any additional findings on the CT scan that can affect the management of the patient.
- The presence or absence of hemorrhage

3. The NINDS Division of Stroke and Trauma

The NINDS provides research funding for the trial, monitors the trial with respect to safety, monitors performance, and gives scientific direction to the trial.

C. Study Administration

1. Steering Committee

The Steering Committee includes principal investigators from each clinical center, the NINDS Project Officer and the Coordinating Center principal investigator and co-principal investigator. The Steering Committee will prepare the final protocol and provide scientific direction for the study at the operational level. The Steering Committee will

advise and assist the Coordinating Center on operational matters, monitor the performance of the clinical centers and receive requests for any proposed ancillary studies. The Steering Committee will also report major problems and recommend changes in the protocol to the Project Officer and the Safety and Data Monitoring Committee. Beyond providing study guidance, the Steering Committee also provides the forum for Principal Investigators to serve as study collaborators.

2. Executive Committee

The Executive Committee consists of the Coordinating Center Principal Investigator and Co-principal Investigator and the Project Officer. The Executive Committee of the Steering Committee will review all unblindings. Where the decision to unblind is not related to an emergency situation, the clinical investigator should discuss the need to unblind with the Executive Committee prior to unblinding.

3. Sub-committees

The Steering Committee will appoint the following subcommittees:

- The **Publications Subcommittee** has established a procedure for reviewing every scientific paper or abstract using unpublished t-PA trial data (including ancillary study data) prior to forwarding the paper for approval by the NINDS. This subcommittee will also review every paper using published t-PA trial data which purports to represent official t-PA trial views or policy. This policy applies to papers prepared for publication or oral presentation. The subcommittee will also review ancillary studies to ensure patient safety, trial design and scientific integrity are not compromised prior to submitting the study to the Steering Committee for review and the NINDS for approval.
- The **Quality Assurance Subcommittee** will monitor the performance of the clinical centers, Coordinating Center, central laboratory and CT reading center. Outcome data is not reviewed by this subcommittee. The NINDS will appoint an independent board to monitor all aspects of the trial.
- The **Stroke Scale Subcommittee** will address issues relating to the reliability, validity, and redundancy in the NIH Stroke Scale and other measures of neurologic function. The subcommittee will also develop definitions for the manual of procedures and address procedural questions relating to the scales throughout the trial.

4. Safety and Data Monitoring Committee

The Safety and Data Monitoring Committee will act in an advisory capacity to the NINDS on policy matters throughout the trial. This group also periodically reviews trial results and reports of adverse effects. The Board is selected by the NINDS and is comprised of members who are not trial investigators. Board meetings are attended,

when appropriate, by senior investigators from the Coordinating Center including the principal investigator, co-investigator and other Coordinating Center investigators as necessary. The Board will review the final protocol, review any subsequent changes to the protocol including any necessary changes to the dose schedule, and make recommendations on early termination of the trial (if appropriate). The Board will also review clinical center performance, make recommendations and assist in resolution of problems reported by the Steering Committee.

5. Clinical Coordinators' Committee

The Clinical Coordinators' Committee will discuss issues relevant to patient management and data reporting. This committee is composed of all the clinical coordinators from the clinical centers and the clinical coordinator from the Coordinating Center.

6. Recruitment Coordinators' Committee

The Recruitment Coordinators' Committee will discuss issues relevant to community education and patient recruitment. This committee is composed of all the patient recruitment coordinators from the clinical centers and the coordinator and health educators from the Coordinating Center.

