The goals of the NINDS t-PA Stroke Trial are stated both as primary and secondary hypotheses. The clinical investigators, without knowledge of any treatment comparisons from Part A of this trial, chose the Barthel Index as the primary indicator of clinical efficacy. The independent Safety and Data Monitoring Committee at the request of the FDA and the clinical investigators have reviewed the outcome data from Part A. They have recommended that further supporting evidence be required, namely, that the primary endpoint be a consistent and persuasive difference between the t-PA treatment group and placebo group enrolled within 180 minutes of stroke onset as defined below under Primary Hypothesis 1. Also specified are sub-group hypotheses to be tested by comparison of outcomes in particular strata within the study population.

A. Primary Hypothesis

There is a consistent and persuasive difference between the rt-PA treatment group and placebo group enrolled in Part B within 180 minutes of stroke onset in the proportion with a 90 day:

Barthel Index ≥ 95

Rankin Score of "no significant disability or symptoms"

Glasgow Outcome Score of "good recovery"

and

NIH Stroke Scale of ≤ 1

B. Secondary Hypotheses

1. There is a consistent and persuasive difference between the rt-PA treatment group and placebo group enrolled within 90 minutes of stroke onset in the proportion with a 90 day:

Barthel Index ≥ 95

Rankin Score of "no significant disability or symptoms"

Glasgow Outcome Score of "good recovery"

and

NIH Stroke Scale of ≤ 1

2. There is a consistent and persuasive difference between the rt-PA treatment group and placebo group enrolled between 91 and 180 minutes of stroke onset in the proportion with a 90 day:

Barthel Index ≥ 95

Rankin Score of "no significant disability or symptoms"

Glasgow Outcome Score of "good recovery"

and

NIH Stroke Scale of ≤ 1

3. There is a difference between the rt-PA treated group and placebo group

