The target population for the rt-PA trial includes men and women aged 18 and older admitted to a hospital emergency room with a confirmed ischemic stroke and able to begin treatment within 180 minutes of onset of symptoms. Every effort will be made to include women and minorities in the trial. Also included in the target population are patients in the same age group who have a stroke while already hospitalized. Patients who have contraindications to the use of rt-PA or other conditions thought likely to impair follow-up to three months will not be eligible for the study.

After completion of baseline examination, required laboratory tests, CT scan, informed consent, and randomization, rt-PA treatment will be initiated in eligible patients. Patients will be followed for one year.

Specifications for the estimation of sample size for the study are given in Appendix A.

B. Enrollment

1. Recruitment

All centers will have a recruitment coordinator who will be responsible for enhancing efforts to recruit stroke patients soon after onset of symptoms. This person will be responsible for coordinating education of local communities and physicians. The goal of the educators program will be to encourage early presentation to the emergency department following the onset of stroke. There will also be education of prehospital care providers about the nature of the t-PA trial and their role in providing early assessment and transport.

2. Eligibility Assessment

a. Patient Log

For the purpose of documenting the emergency room and hospital population from which the patients in this trial are drawn, each clinical center will maintain a log of all patients with ischemic and hemorrhagic stroke presenting within 24 hours of the onset of their symptoms. This information will be helpful in planning the recruitment of patients if there is a future Phase III trial. Included in the log will be information regarding the

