3. Time of onset well-established to be less than 90 minutes before treatment would begin, or time of onset well-established to be less than 180 minutes before treatment would begin and the total number of patients at the Clinical Center that have been treated within 180 minutes from onset does not exceed by more than 2 the number of patients treated within 90 minutes.

c. Exclusion Criteria

Patients are not eligible when any of the following exclusion conditions apply:

1. Patient has (a) only minor stroke symptoms or (b) major symptoms which are rapidly improving by the time of randomization.
2. There is evidence of intracranial hemorrhage on CT scan.
3. Patient has a clinical presentation that suggests subarachnoid hemorrhage, even if the initial CT scan is normal.
4. Patient is a female and lactating or known or suspected to be pregnant.
5. Patient has platelet count less than 100,000, prothrombin time greater than 15, patient has received heparin within 48 hours and has an elevated partial thromboplastin time (> upper limit of normal for each laboratory) or patient is currently taking oral anticoagulants.
6. Patient has had major surgery or serious trauma excluding head trauma in the previous 14 days or serious head trauma in the previous 3 months.
7. Patient has history of gastrointestinal or urinary tract hemorrhage in previous 21 days.
8. Patient has had arterial puncture at a non-compressible site or a lumbar puncture in the previous 7 days.
9. On repeated measurement, patient has a systolic blood pressure > 185 or diastolic blood pressure > 110 at the time treatment is to begin or patient requires aggressive treatment to reduce blood pressure to within these limits.
10. Patient has a history of stroke in the previous 3 months or has ever had a intracranial hemorrhage considered to put the individual at an increased risk for intracranial hemorrhage.
11. Patient has a serious medical illness that is likely to interfere with this trial.
12. Patient has abnormal blood glucose (< 50 or > 400 mg/dl).
13. Patient has clinical presentation consistent with acute myocardial infarction or patient has a clinical presentation suggesting post-myocardial infarction pericarditis.
14. Patient who in the judgement of the investigator cannot be followed for three months.
15. Patient had a seizure at onset of stroke.

d. Informed Consent

Informed consent will be obtained prior to randomization.

3. Baseline

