Upon notification that a patient has been enrolled in the study, the Coordinating Center will transmit a patient follow-up schedule to the Clinical Center. The patient follow-up schedule is given in the manual of procedures. The NIH stroke scale will be completed at 2 hours after initiation of treatment, and at 24 hours (\pm 20 minutes), 7-10 days and 3 months (\pm 2 weeks) after onset of stroke. Also a Glasgow outcome score will be completed at 3 months. The Barthel Index should be completed at 7-10 days and 3 months. A modified Rankin will be completed to describe the patient's condition prior to stroke and at 7-10 days and 3 months. Follow up CT scans will be performed at 24 hours, 7-10 days and 3 months after onset of symptoms. In addition to baseline, blood will be drawn for analysis of fibrinogen and fibrinogen degradation products at 2 hours after treatment initiation and 24 hours post stroke onset. Other follow-up data to be collected are discussed in the manual of procedures.

After the 3 month visit, all patients will continue to be followed and a health history questionnaire will be completed at six months and one year.

3. General Patient Management Guidelines and Other Therapy

For all patients:

- a. Admission to a Neurology Special Care area or Intensive Care Unit.
- b. Therapy for acute stroke other than rt-PA (including heparin or antiplatelet

drugs) will not be initiated during the infusion or for 24 hours following the onset of symptoms (see C.4).

- c. Supplemental oxygen as indicated.
- d. Initially NPO; later, diet as tolerated and no nasogastric tube (NGT) for at least 24 hours except when clinically indicated and no other less invasive option is available.
- e. IV fluids to maintain adequate urine output during the first 24 hours.
- f. Cardiac Monitoring.
- g. Blood pressure monitoring and appropriate measures to control BP within acceptable limits.
- h. Central venous pressures, pulmonary artery pressure, and cardiac output monitored as indicated but not prior to, during the 60 minute rt-PA infusion, or for 30 minutes following the end of rt-PA infusion unless an emergency situation intervenes. Pre-existing peripheral lines may be maintained but will be closely watched and compressed if removed.

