The primary hypothesis will be tested with a global statistic (Wald test) computed using generalized estimating equations as described by Lefkopoulo, Moore, and Ryan (30). The stratifying variables, center and time (≤ 90 , $< 91-180$ minutes from stroke onset) will be included in the model as covariates. This global test statistic was chosen because it will test the consistency in direction of all four functional outcome measures specified in the primary hypothesis. The critical level for the test will be 0.05. All patients randomized to Part B will be included in the primary analysis. Treatment failure will be ascribed to any who have died before an outcome was determined and to any who could not have an outcome determined, regardless of the reason.

If after the global test statistic is computed, the differences between treatment groups are found to be statistically significant, then further testing will be done using logistic regression with center and time as covariates at the 0.05 level for each of the four functional scales used in the global test. The purpose of this testing is to describe the effect of treatment on each of the functional scales.

An interim analysis using the primary outcome will be carried out once during the trial as requested by the Data Monitoring and Safety Committee. Critical levels will be adjusted using the methods of Lan and DeMets (21) with an O'Brien and Fleming spending function. More frequent interim analysis of adverse events, especially death and hemorrhage will be carried out in conjunction with the Monitoring Committee. The

results of any interim analysis of adverse event or any outcome will be seen only by the trial statisticians and the Monitoring Committee. Any decision to stop the trial for safety or efficacy will not be based solely on statistical considerations.

E. Authorship of Papers

As previously agreed any publications or presentations of data on trial patients must have the permission of the NINDS. Also centers are not to separately present or publish data relating to the objectives of the trial. The NINDS t-PA Stroke Trial Group will be listed as author on major trial publications. Investigators, the NINDS project officer, and committees will be listed at the end of the paper.

VI. Organizational Structure

A. Introduction

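### Part B scores success as an absolute near-normal state and admits patients with pre-stroke disability, yet the pre-stroke Rankin it collects has no role in the primary or per-scale models

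*Supplement*

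**What the plan says.** **Endpoint.** Part B, III.A names four 90-day outcomes, each with a fixed cut-off: "Barthel Index ≥ 95", a Rankin of "no significant disability or symptoms", the top Glasgow category, and an NIH Stroke Scale of 1 or less. None refers to the patient's state before the stroke.

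**Test.** V.D combines the four as separate correlated binary outcomes in a GEE global Wald test. If that is significant, a logistic model follows for each scale. "The stratifying variables, center and time" are the only covariates named, in the GEE model and in the four logistic models alike. All patients randomized to Part B are analyzed, and deaths and undetermined outcomes count as failures.

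**Who can enter.** IV.B.2 sets a lower age limit but no upper one, and no limit on prior function. Exclusion 10 covers "Patient has a history of stroke in the previous 3 months" (and certain past intracranial hemorrhages), so an older ischemic stroke with residual deficit does not exclude. IV.A includes "patients in the same age group who have a stroke while already hospitalized". Exclusion 11, on serious medical illness, is discretionary and not about disability.

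**What is collected.** IV.C.2: "A modified Rankin will be completed to describe the patient's condition prior to stroke". This value is not a randomization stratum (IV.B.4), a covariate (V.D) or a listed sub-group hypothesis (III.C).

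**The concern.** Part B asks whether rt-PA reverses the disability of the present stroke. A patient left with a hemiparesis a year earlier could recover fully from the new event and still be scored a failure on Rankin, and probably on the other scales. Such patients add failures to both arms. They shrink the absolute difference and add noise that a baseline value already in hand could remove. Prior disability is not a randomization stratum, so the arms may also differ in it by chance, and the planned models would leave that difference in the estimate.

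The baseline NIH Stroke Scale is not a substitute. It mixes old and new deficit and does not show who started below the success level.

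**Working it through.** **Inputs from the documents.** 160 per group and two-sided alpha 0.05 (Part B, Appendix A). Part B's text gives no numerical power, effect size or control rate; its power curves are in a figure not shown.

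**Assumptions.** Success of 30% v 45% among patients able to succeed, and a share f of 5-20% who cannot succeed in either arm. None of these figures is in the documents.

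**Calibration on Part A.** Part A's appendix uses the arcsine approximation. For 140 per group, 40% v 20%, it states 0.95; I get 0.959. For 70 per group, 40% v 16%, it states 0.90; I get 0.898. Both reproduce.

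**Step 1, planned analysis.** Each arm's rate is multiplied by (1 − f), with n = 160:

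power = Φ{ [ |p₂ − p₁|·√n − 1.96·√(2p̄(1 − p̄)) ] / √(p₁(1 − p₁) + p₂(1 − p₂)) }

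At f = 10%: p₁ = 0.27, p₂ = 0.405, p̄ = 0.3375. The numerator is 0.135 × 12.649 − 1.96 × 0.6687 = 0.397, the denominator is 0.6619, and Φ(0.600) = 0.73.

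**Step 2, affected patients separated.** If pre-stroke Rankin identified them perfectly, the information would come from 160(1 − f) per arm at 30% v 45%. At f = 10%, n = 144: (0.15 × 12 − 1.96 × 0.6847)/0.6764 = 0.677, and Φ(0.677) = 0.75.

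| f | rates | difference (points) | power, planned | power, separated | gain (points, before rounding) |
|---|---|---|---|---|---|
| 0 | 30.0% v 45.0% | 15.0 | 0.79 | 0.79 | 0 |
| 5% | 28.5% v 42.75% | 14.25 | 0.76 | 0.77 | 1.2 |
| 10% | 27.0% v 40.5% | 13.5 | 0.73 | 0.75 | 2.5 |
| 15% | 25.5% v 38.25% | 12.75 | 0.69 | 0.73 | 3.8 |
| 20% | 24.0% v 36.0% | 12.0 | 0.65 | 0.70 | 5.0 |

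The last column is what adjustment can buy. The rest of the fall from 0.79 comes from having fewer informative patients, which no analysis wording restores.

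**Step 3, scale of effect.** In this model the risk ratio stays at 1.50. The odds ratio moves from 1.91 at f = 0 to 1.84 at 10% and 1.78 at 20%.

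**Step 4, chance imbalance at f = 10%.** The between-arm difference in the share affected has SD √(2 × 0.10 × 0.90/160) = 3.4 points. At its 95% limit that is about 6.6 points. Multiplied by the average success rate among those able, (0.30 + 0.45)/2 = 0.375, the estimated difference shifts by about 2.5 points.

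**The case against.** The strongest reply is that V.D does not define an all-four composite. A reader might infer from the list in III.A that a patient must meet every cut-off and that anyone with prior disability is a certain failure. The GEE test scores each scale separately, and a patient disabled for a non-neurological reason can still reach an NIH Stroke Scale of 1 or less. Only the Rankin level is out of reach almost by definition. This stands, and it makes the table an upper bound, because the model sets success to zero on the whole endpoint.

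Second, the calculation is univariate, and Appendix A expects the global test to have more power. Adjusting only for the stratification factors is also a standard choice. Both points are fair; they reduce the importance of the point but give no reason to leave a collected baseline value unused.

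Third, other outcomes avoid the near-normal threshold: change in the NIH Stroke Scale, median Rankin and Glasgow, and infarct volume (III.B). They are secondary and do not help the primary test. The discretionary illness exclusion may remove some affected patients, but how many cannot be known.

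Fourth, if the disabled stratum has no successes, its coefficient has no finite estimate in a logistic or GEE fit, and its patients then add nothing to the treatment estimate. That is a real technical difficulty and needs a stated fallback. It does not remove anyone from the analysis set: a stratum that fails entirely in both arms carries no information on relative effect.

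**Conclusion.** The point holds as a modest loss of efficiency and interpretability. Recovery from the new stroke can go unregistered in patients who began below the success level, and the variable that identifies them is collected without a stated use. Under the assumed 30% v 45% with 160 per arm, adjustment recovers at most about 1 to 2.5 power points for f of 5-10% and about 4 to 5 for f of 15-20%. It also removes imbalance shifts of the order of 2.5 points at f = 10%. All of this depends on f, which the documents do not give.

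Two stronger readings are not supported. A reader might infer that the treatment comparison is biased; randomization keeps the test valid, and in this model the risk ratio is unchanged and the odds ratio moves little. A reader might also charge the whole drop from 0.79 to 0.65 at f = 20% to the missing covariate; only 5 of those points are recoverable by adjustment.

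**What to change.** In Part B, V.D:

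- Add pre-stroke modified Rankin (at or better than the primary success level v worse) as a covariate in the GEE model and the four logistic models. Say whether its coefficient is common to the four scales or scale-specific.
- State the fallback if the worse stratum has no successes, for example a stratified score or Mantel-Haenszel analysis, or a penalized fit.
- Pre-specify one supporting run of the same global test in patients whose pre-stroke Rankin meets the success level.

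Eligibility, primary population, endpoint and alpha do not change.

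The cost is plan wording, fixed before any unblinded Part B analysis. The main drawback is timing. IV.C.2 does not say when the pre-stroke Rankin is recorded, and a patient counts as randomized only when the infusion begins, so it may be scored after treatment starts. The plan should ask for it as early as possible and in any case before the 24-hour examination, with missing values kept as their own category.

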Prior to randomization blood must be drawn for later analysis of fibrinogen and fibrinogen degradation products. Also a baseline NIH stroke scale should be obtained. As soon as possible after randomization, additional data should be obtained as described in the manual of procedures.

4. Randomization

A stratified blocked randomization will be used to assign patients to rt-PA or placebo. The strata will include clinical center and time from onset of symptoms (≤ 90 , >90 minutes to ≤ 180 minutes). Block size will be varied. Prior to randomization the treating physician must confirm that the patient meets eligibility criteria.

Because of the limited time available for randomization, randomization will take place at the hospital where treatment will be given. The medication, rt-PA must be obtainable 24 hours a day in order to guarantee drug availability. A patient is considered randomized and in the trial at the time infusion of trial medication begins.

Within the first two hours of administration of the trial medication, the Coordinating Center must be called and given the time, date, location, study ID number, date of birth, sex and race of the patient. The Clinical Center must also keep a careful inventory of drugs for the trial and complete the drug accountability form.

5. Unblinding

The trial medication, rt-PA, will be provided by Genentech along with an identically packaged placebo. The Coordinating Center will know the medication assignment for a patient. Each medication package will have a removable label to be opened at the Clinical Center if unblinding is necessary. Conditions requiring unblinding are generally those occurring within a few days of treatment. To unblind, the patient's physician must require knowledge of the drug in order to provide appropriate patient care. Additionally, because the clinical centers will be carrying out laboratory analyses which may provide information which will unblind, procedures for storing this information as described in the manual of procedures must be followed.

For some conditions such as myocardial infarction or surgery, unblinding the specialist rather than informing the trial investigator should be considered. The trial investigator would remain blinded.

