APPENDIX

A. Sample Size

Primary Hypothesis

Power curves are provided in Figure 1 for univariate analyses using various rates of success in the control group and various values for the absolute percent difference from control. The absolute percent difference represents the smallest difference detectable with the specified power. Calculations are based on a sample size of 160 per group, the sample size for Part A. The critical level for the test is 0.05 (two-sided). The power for a global test should be greater.

Subgroup Hypotheses

There will generally be lower power to address the subgroup hypotheses.

[figure not shown]

Figure 1. Minimum Absolute Percent Difference Detectable

*Success Rate in Placebo
N=160/group Alpha=0.05, Two-sided

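### The Part B primary and follow-on models leave out the baseline NIH Stroke Scale: a valid test, but one that may give up power and protection against chance severity imbalance

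*Supplement*

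**What the plan says.** Part B, V.D tests the primary hypothesis with a Wald statistic from generalized estimating equations (GEE) over four binary 90-day outcomes. Of "The stratifying variables, center and time" it says that they "will be included in the model as covariates". If the global test is significant, the plan moves to "logistic regression with center and time as covariates at the 0.05 level for each of the four functional scales". Every patient randomized to Part B is to be analyzed, and an undetermined outcome counts as failure.

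On severity, Part B, IV.B.3 says "Also a baseline NIH stroke scale should be obtained", under the heading of what is done before randomization. Under IV.B.4, "The strata will include clinical center and time from onset of symptoms"; severity is not a stratum. In Part B the baseline score serves only as the reference point for early change-from-baseline outcomes and for one change-score subgroup hypothesis. V.D contains no severity-adjusted analysis, primary or supportive. A general remark about multivariate analyses appears only in Part A, V.D, and it names no covariate.

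**The concern.** The four primary outcomes (III.A) are states close to full recovery: Barthel at least 95, NIH Stroke Scale at most 1, and the best Rankin and Glasgow categories. They are absolute states, so a patient's starting severity is not taken out of them, and one of them is the same scale that is measured at entry. Eligibility sets no upper limit on severity. Severity may therefore carry much of the outcome variation, and it is balanced neither by the randomization nor by the model.

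Two things would be at stake: power of the global test, and the credibility of the estimate if the arms happen to differ in severity. The second matters most for the two secondary comparisons by time group, where the arms are half as large.

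**Working it through.** **Inputs from the documents.** Part B has 320 patients, 160 per group (Part B, I and Appendix A). "The critical level for the test will be 0.05" (V.D); Appendix A makes it two-sided. There are eight centers and two time groups. Part B's power curves are in a figure that is not available, so no stated Part B power can be checked.

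**Reproducing the plan's own power figures (Part A Appendix).** The arcsine formula is power = Φ(h√(n/2) − 1.96), with h = 2 asin√p₁ − 2 asin√p₂.
- 40% v 20%, n = 140: h = 0.442, and 0.442 × √70 − 1.96 = 1.74, so power is 0.959 (stated 0.95).
- 40% v 16%, n = 70: h = 0.546, and 0.546 × √35 − 1.96 = 1.27, so power is 0.898 (stated 0.90).

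Both agree. The same formula at 160 per group gives single-scale detectable differences at 80% power of 13.8, 15.1 and 15.6 points for placebo rates of 20%, 30% and 40%.

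**Power with and without baseline severity.** The planned test was simulated with 160 per arm, four correlated binary outcomes, a common treatment effect, independence working correlation and a robust Wald test, with center and time as covariates. Assumptions not in the documents: 30% placebo success on each scale, a marginal odds ratio of 1.7, and a standardized severity score of varying strength. An odds ratio of 1.7 takes odds of 0.30/0.70 = 0.429 to 0.729, that is 42.1% success, a difference of about 12 points. There were 2,500 trials per row.

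| Severity log-odds per SD (odds ratio) | Without | With | Gain, points |
|---|---|---|---|
| 0 (1.0) | 0.788 | 0.789 | 0.1 |
| 0.4 (1.5) | 0.797 | 0.813 | 1.6 |
| 0.8 (2.2) | 0.773 | 0.831 | 5.8 |
| 1.2 (3.3) | 0.747 | 0.876 | 12.9 |

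For larger effects (those with 80% single-scale power), global power is already 0.91 to 0.93 without the covariate and becomes 0.94 to 0.97 with it, over strengths 0.4 to 1.2.

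**Type I error.** At strength 0.8, with 3,000 trials, it is 0.054 without and 0.051 with the covariate.

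**Chance imbalance.** The between-arm difference in mean severity, in SD units, has standard error √(2/n).
- Overall: √(2/160) = 0.112; 0.2/0.112 = 1.79; two-sided probability about 7%.
- Within a time group of 80 per arm (320 split evenly by time and arm): √(2/80) = 0.158; 0.2/0.158 = 1.26; about 21%.

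**Effect of an imbalance on the estimate.** In the simulated trials the unadjusted log odds ratio moved by 0.37, 0.69 and 0.95 per SD of imbalance at strengths 0.4, 0.8 and 1.2. At the overall 95% limit, 1.96 × 0.112 = 0.22 SD, the odds ratio shifts by a factor of exp(0.22 × 0.37) = 1.08, exp(0.22 × 0.69) = 1.16 or exp(0.22 × 0.95) = 1.23. With severity in the model the corresponding slope was at most 0.04.

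**The case against.** The strongest reply is that nothing is broken. The model is pre-specified, it contains the stratification factors, and it uses every randomized patient. A reader might infer that omitting severity biases the trial or invalidates the test. It does not: chance imbalance is already part of the 5% error rate, can favor either arm, and stays within 0.2 SD overall in about 93% of trials. This stands.

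A reader might also take strong prognosis as given. The documents provide no figure. The nearest text, Part B secondary hypothesis 13, concerns the 24-hour score, not the baseline one, and poses the correlation as a hypothesis. The exclusion of minor and rapidly improving strokes narrows the severity range somewhat. A large power loss therefore cannot be asserted, and the weak case belongs in the range.

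Nor do the documents guarantee a baseline score for every patient. IV.B.3 says it should be obtained, while the accompanying blood draw must be. The pre-stroke Rankin ("A modified Rankin will be completed to describe the patient's condition prior to stroke") has no stated timing before randomization, so it is a weaker candidate.

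Finally, no separate analysis plan is shown, and supportive adjusted analyses are often left to one. That answers the lack of a supportive analysis. It does not answer the choice of primary model, because V.D itself names the covariates.

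**Conclusion.** The point holds as a matter of efficiency and protection, not validity. The Part B primary and follow-on models omit a baseline measure that the protocol plans to collect before randomization and that the design does not balance. Under the stated assumptions (30% placebo success, marginal odds ratio 1.7, common effect across scales), the gain from including it runs from about 0 to 2 points of power if severity is weakly prognostic, through 6, to 13 if strongly prognostic. Type I error is unaffected. The imbalance probabilities, 7% overall and 21% within a time group, rest only on the sample size and an even split. How far such an imbalance would move the result again depends on the unknown prognostic strength. The change is worth making because it costs little and, in these simulations, loses no power even when severity carries no information.

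**What to change.** Amend Part B, V.D as follows.
- Name baseline NIH Stroke Scale, as a linear term, as a covariate alongside center and time group in the primary GEE model and the four logistic models. Use it alongside center in the ≤90 and 91-180 minute analyses too, keeping whatever other terms those models have.
- State a simple rule for a missing baseline score, for example single imputation from baseline data blind to treatment, so that all randomized patients stay in. State also how unevaluable items enter the score, since a Part B subgroup hypothesis divides by the number of evaluable items.
- Report the center-and-time-only model as supportive.
- Leave no optional covariates open.

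Timing matters. V.D plans one interim analysis of the primary outcome, seen by the trial statisticians, and IV.B.5 leaves the Coordinating Center biostatisticians unblinded to the Part A analysis. The change should therefore be fixed before any unblinded interim look, by people who have not used Part A or Part B treatment comparisons.

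The cost is a few sentences and no new data. The one small downside is that the odds ratio becomes conditional on severity. In the simulated scenario a marginal 1.7 corresponds to conditional log odds ratios of 0.55, 0.60 and 0.67, that is about 1.73, 1.82 and 1.95 at strengths 0.4, 0.8 and 1.2, so the report should say which is shown.
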